Nonetheless, several approaches have been described in addition to the immediate implant placement for contouring the socket alterations caused by tooth extraction: positioning of the implant on the palatal wall; performing the surgery using the flapless technique to maintain vascularization; and using soft tissue or bone grafts to maintain the dimension of the ridge by socket augmentation. [33]

Guided bone regeneration (GBR) provides an evidence-based treatment modality for enabling predictable accommodation of dental implants with excellent long-term survival rates [49-51]. While autologous bone remains the gold standard among the biomaterials used for bone regeneration [52-54], limitations have also been reported including a second surgical site, additional morbidity, chance of complications to the harvested site, and faster than ideal resorption rates [51, 55]. The phenomenon of bone regeneration along with the removal of all the extra-skeletal non-osteogenic cells from an osseous defect is widely established in implant dentistry. [40] Several animal and clinical trials have demonstrated the efficacy of using regenerative procedures around immediately placed dental implants using a variety of materials. [39, 40-47] These publications have reported the stability of the regenerated hard tissues over time and their ability to provide support and aid in functioning of osseo-integrated implants. Hard tissue

reconstruction is facilitated by guided bone regeneration through prevention of epithelial cell migration in the defect area. The rate of osteogenesis extending inward from the adjacent bony margins should be greater than the rate of fibrogenesis growing in from the surrounding soft tissue. [48]

Commercially available bone substitute materials are most frequently available in a particulate form and are easy to disperse, making it difficult to adequately graft the particles in the bone defect and to maintain the desired shape of the rebuilt area. Furthermore, the majority of commercially available bone grafting materials (allografts, xenografts or synthetic alloplasts) contain only scaffolds for osteoconductive application, lacking osteoinductive factors such as living cells and growth factors [55]. A frequently used, thermally regulated, bone grafting material is the Deproteinized Bovine Bone Mineral (DBBM; owing to its lack of proteins/growth factors) or An-organic Bovine Bone Mineral (ABBM; owing to its lack of organic components) [56, 57].

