The main objective of immediate implant placement is to provide an osseointegrated fixture suitable for an aesthetic and functional restoration. Bone fill in the gap between the implant and the surrounding bone is important. The buccal aspect of an implant is of great concern, especially in the esthetic zone, because the buccal bony plate is usually thin [62,63] and its resorption can result in soft tissue recession. [64]

Sohn et al. reported that sticky bone is easy to make and they are a very effective materials for the reconstruction of edentulous alveolar bone defect, based on the concept of minimally invasiveness on ridge augmentation.[27]

7. Objectives:

Primary objectives:

The primary objective of this study is to clinically assess pink esthetic score following Buccal Plate Augmentation using Sticky Bone Versus usage of sticky bone as a jumping gap filling material with simultaneous immediate implant placement in the maxillary esthetic zone.

Secondary objectives:

The secondary objectives of this study are to measure and assess :

- Crestal bone level .
- Thickness of labial plate of bone .
- Soft tissue profile /contour .
- Patient satisfaction .

Hypothesis:

Null hypothesis: there is no difference between pink esthetic score following buccal plate augmentation using sticky bone and that following sticky bone used to fill the jumping gap with simultaneous immediate implant placement in maxillary esthetic zone.

8. Trial design:

this trial is a randomized controlled clinical trial, two arms superiority trial with 1:1 Allocation.

III. Methods

A) Participants, interventions & outcomes

9. Study settings:

- The study is to be conducted in the Oral Medicine and Periodontology department, Faculty of Dentistry, Cairo University, Egypt.
- Patients are to be selected from the outpatient clinic of the department of Oral Medicine and Periodontology, Cairo University.

10. Eligibility criteria:[68]

Inclusion criteria:

- Patients aged 18 years or older.
- Presence of a non-restorable maxillary tooth in the esthetic zone including maxillary anteriors and premolars indicated for extraction.
- An intact buccal plate of bone after extraction.
- Full-mouth plaque and bleeding score not exceeding 20%.
- Patients showing motivation to comply with post-operative care instructions and follow-up appointments.

Exclusion criteria:

- Periapical infection involving the tooth to be extracted.
- Periodontal disease

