- Systemic health conditions that contraindicate or affect healing of implant surgery (Diabetes Mellitus, Leukemia)
- Pregnant and nursing females.
- Smokers.

11. Interventions

Preoperative phase:

All patients will undergo pre-operative clinical examination: Patient's data will be collected; name, gender and age, medical and dental histories will be taken. Also, all patients will undergo standardized periapical radiograph to detect any pathosis and a pre-operative Cone beam computed tomography (CBCT) scans will be taken to evaluate the tooth root configuration and to confirm the presence of intact buccal wall, Vital structures related to the tooth, Vertical and horizontal dimensions of the alveolar bone and Bone density.[68]

Patient preparation for surgical procedure:

After extra oral disinfection of the surgical site, the patients will be asked to rinse their mouths with Chlorohexidine HCL 1.25% mouthwash (Orovex mouthwash, Macro group, Egypt) immediately preoperatively. Local infiltration anesthesia [Articaine 4% 1:100,000 epinephrine] (Artinibsa 40mg/0.1 mg/ML - epinephrine 1:100000, Spain) will be used for all procedures.[68]

Control group:

- The surgical procedure will be performed in sterile surgical field. Under local anesthesia, sharp dissection of the supracrestal fibers will be done with no.15 c scalpel blade. With the purpose of preserving the buccal and palatal bone walls, periomes, elevators and maxillary root forceps will be used to facilitate atraumatic extraction.
- The socket will be well irrigated with saline and debrided with a bone curette. An intact buccal bone plate should be found after extraction of the tooth.
- Bony sockets will be prepared through sequential drilling for the placement of the implant.
- Achieving primary stability after implant placement will be followed by placement of cover screw.
- Venous blood will be withdrawn under aseptic conditions by veni puncture of the antecubital vein and transferred into sterile tubes which will be devoid of anticoagulants. I- PRF preparation will be done using the protocol developed by Mourão et al. [67]
- Plastic PET tubes to create Liquid-PRF, while glass tubes will be used to obtain Solid-PRF.
- Blood will be centrifuged at a speed of 3000 rpm for 10 minutes to obtain autologous PRF plug.

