- Blood will be centrifuged at a speed of 700 rpm for 3 minutes. An orange- colored fluid will be formed as the upper layer in the test tubes i.e., I- PRF. Approximately 1 ml of I-PRF will be collected in a syringe.
- Solid-PRF + Liquid-PRF mixed DBBM: Solid-PRF membranes will be mixed thoroughly with 0.25 g of DBBM particles. Then 1 mL Liquid PRF from the buffy coat layers will be added drop by drop to the DBBM.
- Following polymerization by 15-20 minutes, sticky bone will be ready to be grafted.
- The sticky bone graft will be condensed and adapted into the jumping gap as well as over the implants.
- the healing abutment will be screwed into the implant body .

Intervention group:

- A thin periosteal elevator will be used to reflect the soft tissue buccal to the bony buccal plate on the mid-facial aspect of the socket in a full-thickness manner, following a corono-apical direction, thereby creating a ‘surgical pouch’.
- The dissection will be advanced beyond the mucogingival line to approximately two-thirds the depth of the socket, and the ‘pouch’ will be expanded in the mesio-distal direction to stretch the soft tissues away from the underlying bony plate.
- Sticky bone will be inserted into the pouch by a mean of a small periosteal elevator. Additional graft material will be added and compressed until adequate filling of the pouch is achieved without overstressing the soft tissues.
- the healing abutment will be screwed into the implant body .

Postoperative Care:

Administration of:

- 1 gm Amoxicillin 500 mg (Misr Co. for Pharmaceutical Industries, Egypt) three times a day for seven days, or doxycycline 100 mg (Nile Co. for Pharmaceuticals and Chemical Industries, Egypt) twice a day if they are penicillin sensitive. [68]
- Ibuprofen 400 mg (Brufen, Kahira Pharmaceuticals, Egypt) will be provided for severe pain. [68]
- 0.12% Chlorhexidine mouthwash twice daily for two weeks. [68]

Patient self-care instructions:

- Avoid any hard brushing and trauma to the surgical site for two weeks.
- Participants will be instructed to avoid causing any damage to the operated site and to avoid consuming hot meals or vigorous rinsing.

Postoperative Radiographs:

- A standardized periapical parallel radiograph will be taken on the same day after implant placement to assess crestal bone level then after 3 and 6 months. CBCT scan will be scheduled for six months postoperative.

12. Outcomes:

PICOT:

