Using CBCT machine . Using the axial view, one reference line will be drawn from the apex of the implant to its platform (long axis); another line, perpendicular to the one at the long axis, will be drawn at the apex of the implant. Parallel to this, two lines will be drawn, one at 1 mm from the implant collar (R1) and another 5 mm apical to it (R2) measuring the thickness of the bone (at the buccal plate) to the nearest 0.1 mm.

Specific measurement time point: baseline and 6 months postoperatively.

4) Soft tissue profile /contour:[69]

Scanning of diagnostic casts by optical scanner.

Specific measurement time point: baseline , 3 and 6 months postoperatively.

14. Sample size:

Pink Esthetic Score (PES) was chosen as the primary outcome variable and effect size was estimated to be 1.5 based on a previous study by Abdelraheem et al (2022). Power calculation was performed at $\alpha=0.05$ and at $\beta=0.20$, equal to 80% of power. Under this assumption, at least 8 patients were needed for each group with a total number of 16 patients. This number was increased to 20 patients (10 patients in each group) to compensate for any possible dropouts.

15. Recruitment:

- Patients will be selected from the outpatient clinic of the Oral Medicine and Periodontology department, Faculty of Dentistry-Cairo University.
- Screening of patients will continue until the target sample is achieved. (Consecutive sampling)

B) Assignment of interventions

16. Allocation:

All patients who provide an informed consent for participation as well as fulfill the inclusion criteria will be included in the study.

16a. Randomization:

Patients will be randomly assigned to either test or control groups using computer generated randomization (www.randomizer.org) which will be performed by the main supervisor.

16b. Allocation concealment mechanism:

Allocation concealment will be done by creating opaque sealed envelopes. The envelope will be chosen by the patient and will only be opened after completion of extraction.

16c. Implementation

- The supervisor will generate the randomization sequence. The principal investigator will enroll the participants.

17. Masking/blinding:

- Blinding of the operator is not applicable.
- Participants, Outcome assessor (primary and secondary outcomes) & biostatistician will be blinded.

C) Data collection, management, and analysis:

18. Data collection methods

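### Section 16b lets the envelope be opened before the implant is placed and stable, so the unblinded operator may do a step both arms need knowing the arm

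*Protocol*

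**What the plan says.** - **Opening of the envelope (Protocol 16b).** "The envelope will be chosen by the patient and will only be opened after completion of extraction". This sets an earliest time. No latest time is given, and there is no link to implant placement.
- **Blinding (Protocol 17).** "Blinding of the operator is not applicable". On the other side, "Participants, Outcome assessor (primary and secondary outcomes) & biostatistician will be blinded".
- **Eligibility (Protocol 10).** One criterion can be settled only during surgery: "An intact buccal plate of bone after extraction". Primary stability is not an eligibility criterion.
- **Implant step (Protocol 11, Control group).** After extraction come debridement, sequential drilling and implant placement, then: "Achieving primary stability after implant placement will be followed by placement of cover screw". No rule covers a site where stability is not reached.
- **Arm-specific steps (Protocol 11).** Control: "The sticky bone graft will be condensed and adapted into the jumping gap as well as over the implants". Intervention: a full-thickness buccal pouch is dissected, and "Sticky bone will be inserted into the pouch by a mean of a small periosteal elevator". The intervention text begins at the pouch and does not say whether the implant is already in place.
- **Implant position (Protocol 6, Review of literature).** Among the approaches to socket changes after extraction the protocol lists "positioning of the implant on the palatal wall".

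**The concern.** Under both the research question and the primary objective, every patient receives an immediate implant. The treatment contrast is what happens to the sticky bone, plus the pouch dissection that one arm requires. An operator must know the arm for those steps. The protocol gives no reason for knowing it while drilling and seating the implant.

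Implant position can plausibly reach the outcomes. PES scores soft-tissue level, soft-tissue contour and alveolar process deficiency. Labial plate thickness is measured from lines set by the implant's long axis and collar. Position also helps determine the width of the jumping gap, which is where the control graft goes. An operator who knows whether that gap will be grafted could, without intending to, place the implant differently in the two arms. The difference would be made at surgery, so a blinded assessor would record it faithfully as a treatment effect.

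The second consequence concerns primary stability. The buccal plate can be inspected before the envelope is opened. If the envelope is opened straight after extraction, stability cannot be checked first, and a site that fails is already randomised.

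**Working it through.** **1. Order of events.** Setting 16b beside section 11:

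| Step | Which arm needs it | Must it precede opening? |
|---|---|---|
| Extraction | both | yes (16b) |
| Check of buccal plate | both (inclusion criterion) | not stated; possible before opening |
| Drilling, implant placement | both (written only under Control group) | not stated |
| Primary stability | both (written only under Control group) | not stated |
| Pouch dissection | intervention | no; arm must be known |
| Sticky bone into gap or pouch | arm-specific | no; arm must be known |

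The two middle rows, implant placement and primary stability, are the exposure: shared by both arms, done by an unblinded operator, and not required to come before opening.

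**2. The plan's own sample size.** Inputs from sections 14 and 20: effect size 1.5 (read as standardised), two-sided α = 0.05, power 80%, 8 per group raised to 10. For a two-sample t-test with n per arm, the noncentrality is d·√(n/2) with 2n − 2 degrees of freedom. At n = 8: 1.5 × √4 = 3.0 on 14 df, critical t = 2.145, power 79.7%. The stated 8 per group reproduces to within rounding. The increase to 10 leaves two spare patients per arm.

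**3. Illustration of the bias.** No true effect, but knowledge of the arm shifts PES by δ SD (an assumption; the document gives no value). With n = 10 per arm, df = 18 and critical t = 2.101, the noncentrality is δ·√5. The rejection probability is P(|T| > 2.101):

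| δ (SD) | noncentrality | false-positive rate |
|---|---|---|
| 0 | 0 | 5.0% |
| 0.2 | 0.447 | 7.1% |
| 0.3 | 0.671 | 9.7% |
| 0.5 | 1.118 | 18.5% |

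**4. Illustration of stability failures.** No failure rate f is given, so a range is assumed. Expected failures are 20f; P(at least one) = 1 − (1 − f)^20. If p₃ is the binomial probability of 3 or more among 10, then P(an arm has fewer than 8 stable sites) = 1 − (1 − p₃)².

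| f | expected of 20 | P(at least one) | P(an arm below 8) |
|---|---|---|---|
| 2% | 0.4 | 33% | 0.2% |
| 5% | 1 | 64% | 2.3% |
| 10% | 2 | 88% | 13.5% |

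The last column affects power only if failures are dropped from the analysis, which the protocol does not say. If they were, power at effect size 1.5 would be 79.7% with 8 per arm and 73.1% with 7 per arm, before any other dropout.

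**The case against.** **The wording is a lower bound.** A reader might infer that the protocol has the envelope opened before the implant is placed. It does not say that: opening after placement would also comply. This objection stands. What remains is that opening at the end of extraction is the natural reading and that nothing rules it out.

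**Stability failures need not be losses.** A reader might infer that patients without primary stability drop out. No rule withdraws them; they could be followed and analysed as randomised, and analysis populations are commonly left to a statistical analysis plan, which is not at hand. This stands too. The point is only that such failures would occur after allocation when they could occur before it.

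**The arms differ by more than graft site, and the shared step is inferred.** The intervention adds a full-thickness dissection, and implant placement is written only under the control heading. Both observations are correct. But both arms are defined by simultaneous immediate implant placement, so the shared step is a safe inference. The order is not: the pouch is described relative to the socket, which is compatible with dissection before the implant is in. If the pouch must come first, the arm must be known by then.

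**Concealment is already sound.** The buccal-plate criterion can be settled before opening, so selective enrolment is not the issue. The operator must know the arm at grafting anyway, so later opening removes only part of the performance risk. Both are true, and neither justifies leaving the avoidable part in place.

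**The sizes are unanchored.** Neither the 0.2 to 0.5 SD shift nor any failure rate comes from the document, and at failure rates of 5% to 10% the expected one or two failures among 20 would fit within the spare patients. The figures show sensitivity, not expected harm.

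**Conclusion.** The point holds in limited form. Section 16b ties opening to extraction alone, so the protocol permits, and on its natural reading implies, that an unblinded operator positions the implant knowing the arm. That is an avoidable performance-bias risk for PES and labial plate thickness.

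The document does not establish that this sequence will be followed, that placement will differ between arms, or that any patient will be lost. Its only support for a link between position and outcome is qualitative: the literature review's mention of implant position and the definitions of the outcomes. The inflation to about 7% to 18.5% depends wholly on the assumed shift of 0.2 to 0.5 SD, and the stability figures depend wholly on the assumed failure rates. No figure in the protocol is shown to be wrong.

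The change should be made because it removes a source of bias at almost no cost, not because a particular bias has been demonstrated.

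**What to change.** 1. **Section 16b:** state that the envelope is opened at the last step common to both arms, after the implant is placed and primary stability has been checked, immediately before the arm-specific pouch or graft step. Sites that fail before that point are logged as screened and not randomised.
2. **Section 11:** set out the common steps once for both arms, and state where pouch creation falls relative to implant placement. That order is the sponsor's to state.
3. **If the pouch must come first:** open the envelope at the latest point that order allows, and keep patients who fail stability after opening in the analysis as randomised.

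**Cost:** a few sentences; no extra patients, staff or visits. The sponsor must confirm the order of the surgical steps. Under item 1, reaching primary stability becomes in effect a condition for randomisation, so it should be added to the eligibility criteria in section 10.

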Buccal plate preservation (BPP) is a technique that has been recently proposed with an aim to reduce the incidence of such resorption. [29]

Buccal plate augmentation (BPA) is a novel approach for ridge preservation aiming to avoid recession of the facial wall of the socket without interfering with the natural healing mechanism of the extraction socket. It consists of placement of bone graft material over an

intact buccal plate, underneath the soft tissues in a surgically created pouch with the aim of maintaining or augmenting soft tissue esthetics of the region [28].

BPP has been previously proposed as an effective alternative to socket grafting and has multiple advantages over the latter including but not limited to the following: (1) does not interfere with the natural, physiological healing of the socket healing process; (2) allows for immediate implant placement; and (3) cost savings since augmenting the labial plate externally requires lesser graft material than intra-socket grafting.[29]

Review of literature:

Tooth loss is a serious health problem that affects an individual's functional abilities, aesthetics, and social interactions. Accordingly, replacing those missing teeth has become a necessity to restore function and esthetics.

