- The phone numbers and address of the patients included in the study will be recorded or extracted from the patients' files.
- The baseline outcomes data as well those at follow-up periods will be assessed by co-supervisor.

Plans to promote participant retention and complete follow- up:

- Telephone numbers of all patients included in the study will be recorded as a part of the written consent.
- All patients will receive a phone call at the time of the pre-determined follow up.

19. Data management:

- All data will be entered and saved electronically.
- Patients' files are to be stored in numerical order and stored in a secured file. Data will be encrypted using a password.
- All data will be maintained after completion of the study.

20. Statistical methods:

Data will be analyzed using IBM SPSS advanced statistics (Statistical Package for Social Sciences), version 21 (SPSS Inc. Chicago, IL). Numerical data will be described as mean and standard deviation or median and range or interquartile range, as appropriate. Categorical data will be described as numbers and percentages. The data will be explored for normality using Kolmogrov-Smirnov test and Shapiro-Wilk test. Comparisons between two groups and over time will be done by 2-way analysis of variance for repeated measures.

If the time factor is not considerable, comparisons between the two groups for normally distributed numeric variables will be done using the Student's t-test while for non- normally distributed numeric variables will be done by Mann-Whitney test.

A p-value less than or equal to 0.05 will be considered statistically significant. All tests will be two-tailed.

D) Data monitoring:

21. Monitoring

No formal data monitoring committee will be needed since it is a study with known minimal risks.

22. Harms

Any temporary or permanent adverse effect will be recorded and documented.

No Harms are expected.

23. Audit

No formal auditing committee is available.

IV. Ethics and dissemination

24. Research ethics approval

This protocol and the template informed consent form will be reviewed by the Ethics Committee of Scientific Research -Faculty of Oral and Dental Medicine, Cairo University.

25. Protocol amendments

Any modifications to the protocol which may have an impact on the conduct of the study, potential benefit of the patient, or may affect patient safety, including changes of study objectives, study design, sample sizes, study

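### Blinding of the CBCT outcomes cannot be assured, and because nothing orders PES before the scan is read, the 6-month PES is exposed too

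*Protocol*

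**What the plan says.** - **Blinding (section 17).** "Blinding of the operator is not applicable", but "Participants, Outcome assessor (primary and secondary outcomes) & biostatistician will be blinded". The claim covers every outcome, with no exception for imaging.
- **Graft site, control arm (section 11).** "The sticky bone graft will be condensed and adapted into the jumping gap as well as over the implants".
- **Graft site, test arm (section 11).** "Sticky bone will be inserted into the pouch by a mean of a small periosteal elevator". The rationale in section 6 defines the technique as graft over an "intact buccal plate, underneath the soft tissues in a surgically created pouch".
- **Imaging (section 11, Postoperative Radiographs).** "CBCT scan will be scheduled for six months postoperative".
- **What is read on CBCT (sections 12 and 13).** Labial plate thickness comes from two lines near the implant collar, "measuring the thickness of the bone (at the buccal plate) to the nearest 0.1 mm". Crestal bone level comes from CBCT with superimposition, at baseline and 6 months; the timeline puts baseline at the preoperative assessment.
- **PES (section 13).** Scored at 3 and 6 months, 0 to 2 points per item and 14 at most, by visual comparison with a reference tooth except for the papillae.
- **Who assesses (section 18).** "The baseline outcomes data as well those at follow-up periods will be assessed by co-supervisor".
- **Roles (section 5).** Both co-supervisors are listed as supervising the surgery and as taking part in randomization and allocation.

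**The concern.** The arms differ in where a bovine bone mineral graft lies relative to the buccal plate, and the CBCT outcomes make the reader look closely at that plate. Coding a scan removes the name but not the anatomy. A reader who never attended surgery may still be able to tell the arm.

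Two things are at stake. First, two of the four secondary outcomes would be reported as assessed blind when the design does not secure it. Second, the same role is given PES and the CBCT outcomes at the same 6-month point, with no order between them. PES is the primary outcome, and 6 months is the time point named in the PICOT. Items such as soft-tissue contour and alveolar process deficiency are judgements that knowledge of a buccal graft could sway.

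**Working it through.** **Step 1: can the scan reveal the arm?** Set the sections side by side.

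| Element | Control | Test |
|---|---|---|
| Graft described inside the socket | yes, in the gap and over the implant | not stated |
| Graft described outside the buccal plate | no | yes, in the pouch |
| 6-month CBCT measured at the buccal plate | yes | yes |

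Whether or not the gap is also filled in the test arm, only that arm is described as having graft outside the plate. Crestal bone level is obtained by superimposing scans, so the reader has the preoperative plate outline to compare with the 6-month image. Mineral beyond that outline would point to the test arm. Superimposition is stated for crestal bone level only, not for thickness.

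**Step 2: can this reach PES?** Three conditions are needed: the same person reads the CBCT and scores PES; that person opens the scan first; the graft can be recognised. Section 18 permits the first, and nothing in sections 13, 17 or 18 prevents the second. The third is the inference from step 1. The only postoperative CBCT is at 6 months, so the 3-month PES is outside this route.

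**Step 3: the plan's own sample size.** Section 14 gives an effect size of 1.5 (read as standardised, since no SD is given), alpha 0.05 and 80% power; section 20 makes tests two-tailed. Exact t-test power is 79.65% at 8 per arm and 88.7% at 10 per arm. The allowance 16/(1 − 0.20) = 20 matches the stated total. The planned 8 per arm therefore reproduces, and this point does not alter it.

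**Step 4: what a biased score would do (illustration).** Suppose there is no true effect and knowledge of the arm shifts the 6-month PES by b SD between arms (assumed; no document gives b). For a two-sided 5% t-test with n per arm, the noncentrality is b × √(n/2) on 2n − 2 degrees of freedom. For b = 0.5 this is 0.5 × √4 = 1.00 at n = 8 and 0.5 × √5 = 1.12 at n = 10.

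| Assumed shift b | False positives, 8 per arm | False positives, 10 per arm |
|---|---|---|
| 0 | 5.0% | 5.0% |
| 0.25 SD | 7.5% | 8.3% |
| 0.50 SD | 15.4% | 18.5% |
| 0.75 SD | 28.7% | 35.5% |

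**Step 5: does that carry over to the planned analysis?** Not directly. Section 20 plans a two-way repeated-measures ANOVA, with a t-test or Mann-Whitney test only if time is not considerable. Shift only the 6-month score by 0.5 SD, take 10 per arm, equal SD at both visits and an assumed correlation r between visits of 0.3 to 0.9.

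- Group main effect (mean of the two visits): standardised shift 0.25/√((1 + r)/2), from 0.31 down to 0.26; rejection 10.1% down to 8.4%.
- Group-by-time term (change between visits): standardised shift 0.5/√(2(1 − r)), from 0.42 up to 1.12; rejection 14.6% up to 65.7%.

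The false-positive rate therefore depends heavily on which term is read as the primary test.

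**The case against.** The strongest objection is that the key fact is not in the protocol. Nowhere does it say that the graft can be told apart from native or healed bone on CBCT at 6 months. A reader might infer from section 17 and the graft sites that CBCT blinding is impossible; the documents do not support that. They support only that it cannot be assured. This part of the objection stands.

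A reader might also infer that the 6-month PES will be unblinded in all 20 patients. That is not supported either. Section 5 lists two co-supervisors, so one role need not be one person, and the order of scan and score is left open rather than fixed the wrong way. The 20 also includes the dropout allowance. This part stands as well, and the PES route is only a possibility.

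The false-positive figures rest on an assumed shift applied as if it affected the whole comparison, and on a test that is not the first-line analysis. They are an illustration, not an estimate.

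Finally, it can be said that the roles in section 5 are a more direct conflict: an assessor who supervised the grafting already knows the arm at every visit and learns nothing from the scan. That is right, and it limits what a scan-order rule can achieve on its own. It does not remove the CBCT point, because an assessor with no part in surgery or allocation would still read the same images.

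**Conclusion.** The point holds in this form: the protocol claims assessor blinding for all primary and secondary outcomes, but its procedures do not secure it for crestal bone level and labial plate thickness, and they leave a route by which the 6-month PES could lose its blinding. It rests on one inference (the graft, or the added contour, is recognisable at 6 months in at least some patients) and, for PES, on one person seeing the scan before scoring. The size is unknown; about 15% (8 per arm) to 18.5% (10 per arm) false positives is what a 6-month t-test would give under an assumed 0.5 SD shift, and that does not transfer directly to the repeated-measures ANOVA. The sample size is unaffected. The remedy is cheap and the primary outcome is a visual judgement, so the change should be made, but this is not evidence that any result would be biased.

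**What to change.** In sections 13 and 17, state that:

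1. the 6-month PES is scored and locked before the postoperative CBCT is opened;
2. the PES scorer has no access to postoperative CBCT images until all PES scores are locked;
3. the CBCT outcomes are then measured from coded scans and reported as not reliably blinded.

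Reconcile sections 5, 17 and 18 on who assesses. Keep the assessor-blinding claim for PES and cast contour only if the assessing co-supervisor takes no part in surgery or allocation for the patients assessed; otherwise drop it. Patient satisfaction is rated by the patient, so it belongs under participant blinding, not assessor blinding.

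Cost: a few sentences and a fixed order at the 6-month visit, with no extra visit or scan. CBCT measurement waits until PES is locked, and the blinding statement becomes less favourable. If neither co-supervisor can stay out of surgery and allocation, keeping the claim for PES and cast contour requires another assessor.
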